#### 5.0 Procedures Involved

#### 5.1 Study Design:

Subjects will perform voice production tasks before, during and after vibration. The subject will wear the collar around their neck. Two lightweight, low voltage, non-invasive surface electrical vibratory motors that are embedded in the wearable collar will be positioned on the skin of the anterior portion of the neck adjacent to the voice box to vibrate the larynx (see Fig. 3 for demonstrating the location of vibrators). Voice production before, during, and after the vibration will be recorded via a microphone for subsequent acoustic analysis on voice quality by speech analysis experts. In addition, during voice production, electroencephalography (EEG) will be recorded with a 64-channel system (Active 2 BioSemi B.V., Amsterdam, The Netherlands or the mobile ANT Neuro EEGO EEG System, Hengelo, The Netherlands) at a sampling frequency of 512 Hz. Subjects will wear a regular head cap arranged in the standard 10-20 configuration (see Figure 1). Four additional external electrodes will be used. Two electrodes will be placed above and below the left eye to detect eye movements. Another two electrodes will be attached on bilateral mastoid processes to serve as reference electrodes. A water-based conductive gel is applied between the electrodes and the skin, which can be cleaned easily with water.

Deleted: Figure 1

Page 12 of 27

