#### 5.2 Study Procedures:

Voice assessment. To assess voice quality, participants will perform two voice production tasks. First, they will vocalize the vowels 'ahh' and 'ee'. They will perform each task three times per assessment. Second, they read aloud twenty test sentences. They will repeat these assessments several times during testing (see Fig. 4). The sentence reading task consists of a set of test sentences based on a 20-sentence inventory described by Ludlow et al. as being sensitive to the voice symptoms experienced in SD [2]. Participants will read the sentences at their own comfortable pace and loudness. In addition, participants will rate their perceived effort level of vocalization on an ordinal scale of 0 to 10 (0 being with no effort and 10 being with maximal effort).

Application of laryngeal vibration. Each VTS trial begins with a 10-second rest period, followed by 4 seconds of vocalization. After 2 seconds of vocalization, vibration will set in while the subject continues to vocalize. Thus, each trial has a rest, a vocalization only, and a vocalization + vibration period. Each participant performs 50 trials per set. The timeline of the complete protocol is illustrated in Figure 4. Testing will begin with a pretest voice assessment, followed by two sets comprising the vibration only and vocalization + vibration conditions. The order of the conditions will be counter-balanced between subjects to account for possible order effects. During the vibration only condition, subjects will be silent and are allowed to read for diversion. After each set a 5-min break will be given and fluids will be offered. Voice assessment batteries will be administered after each set. After completion of two sets and final voice assessments are immediately after treatment (Post 2 OFF), and 20 min and 60 min after VTS has stopped (Post 20, Post 60).

Page 13 of 27

Revised: 9/28/2017

#### Deleted: 4

PROTOCOL TITLE: Effect of Short-term Laryngeal Vibration on Voice Quality. Grant title: Feasibility of laryngeal vibration as a treatment for spasmodic dysphonia 01/31/2021

Figure 2 Experimental design for in-person testing.

Usability questionnaire: The last section of study is to ask participants to fill out a questionnaire about the usability of the wearable collar.

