with no effort and 10 being with maximal effort). This concludes the pretest voice assessment (see Fig. 6). Subsequently, participants will apply the laryngeal vibration on themselves as instructed for a period of 10 minutes. A study personnel will instruct the participant for each step of the testing. The voice assessment will be repeated after each set of VTS and twice during the retention period (see Fig. 6) The procedure for remote testing is identical to the in-laboratory visit except it does not include EEG and eye movement recording.

5 min 5 min 10 min 5 min

Figure 6. Experimental design for remote testing.

The recorded voice data will be stored on the voice recorder that was sent to the participant. The voice data are already deidentified. The audio file names do not contain any HIPPA incompliant information. The files names comprise only the subject ID and the session number (i.e prestest, set 1, etc.). Upon completion of the remote testing session, the participant will receive a prepaid shipping label via email. The participant will print the label and send the equipment back to the laboratory, thus there is no shipping cost for the participant

The stored deidentified voice data will be then removed from the voice recorder and will stored separately on a password protected University of Minnesota HIPAA compliant server where in-laboratory testing data is also located.

Usability questionnaire: The last section of study is to ask participants to fill out a questionnaire about the usability of the wearable collar.

5.3 Study Duration:

The study consists of a single session. Total exposure time to vibration will be approximately 30 minutes. Each VTS set will last 20 minutes. There will be 5 minutes breaks between sets. The interspersed, repeated voice assessment will allow to document time-dependent changes in voice quality and cortical activation due to laryngeal vibration up to 60 minutes past VTS application. Total duration of the study will be 115 minutes.

5.4 Individually Identifiable Health Information:

Page 15 of 27

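### The remote procedure is called identical to the laboratory visit, but has a 10-minute vibration period against 20-minute sets and five vowel repetitions against three; the trial timing in 5.2 also needs reconciling with 5.3

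*Combined protocol and SAP*

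**What the plan says.** **Laboratory.** Section 5.2 defines the trial: "Each VTS trial begins with a 10-second rest period, followed by 4 seconds of vocalization. After 2 seconds of vocalization, vibration will set in". It adds "Each participant performs 50 trials per set". The pretest assessment is "followed by two sets comprising the vibration only and vocalization + vibration conditions", and participants are silent in the vibration-only condition. On breaks it says "After each set a 5-min break will be given and fluids will be offered". Each vowel is produced three times per assessment.

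**Duration.** Section 5.3 says "Total exposure time to vibration will be approximately 30 minutes. Each VTS set will last 20 minutes", and then "Total duration of the study will be 115 minutes". It makes no distinction between laboratory and remote sessions.

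**Remote.** The remote-testing part of 5.2 has participants vibrate their own larynx for 10 minutes, with each vowel produced five times at baseline. Assessments follow each set, and two more come in the retention period. It then describes the procedure as identical to the laboratory visit, the only exception being the EEG and eye recordings.

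**Device.** Section 4.1 offers a continuous mode, set for 1 to 20 minutes, and a voice-detection mode. The visible text does not say which mode applies to which set.

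**Analysis.** Section 15.1 plans a MANCOVA on the acoustic variables with pre/post assessment as the factor, followed by univariate repeated-measures ANOVAs. It does not mention testing mode.

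**The concern.** Vibration is the intervention, so its duration is the dose. Staff who follow the remote text will deliver a different dose from staff who follow 5.3, under a protocol that says the two procedures are the same. Section 15.1 would then pool these participants with nothing to mark the difference. The documents give no expected number of remote participants among the planned 20 patients and 20 controls, so the share affected is unknown.

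A related question arises within the laboratory text: whether the trial timing in 5.2 leads to the set length and total exposure in 5.3. Section 1.1 hopes the work will support a later trial on dosage and duration. That trial would start from the dose reported here.

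**Working it through.** **1. Laboratory and remote text side by side**

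| Item | Laboratory (5.2, 5.3) | Remote (5.2) |
|---|---|---|
| Vibration period | 20 min per set, two sets | 10 min; per set or in total not stated in the visible text |
| Total vibration | about 30 min | 10 min, or 2 × 10 = 20 min if per set |
| Repetitions of each vowel | 3 per assessment | 5 at baseline |
| Stated difference | – | EEG and eye recordings only |

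On either reading of the 10 minutes, the remote text matches neither the 20-minute set nor the total of about 30 minutes. This comparison needs no assumption.

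**2. The 115-minute session**

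Assume each voice assessment takes 5 min, and do not count the length of the last one. Pretest 5 + set 20 + assessment 5 + break 5 + set 20 + follow-up 60 = 115 min, which reproduces 5.3. The same layout with two 10-minute sets gives 5 + 10 + 5 + 5 + 10 + 60 = 95 min. Under this assumption the stated session length fits 20-minute sets and does not fit 10-minute remote sets.

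**3. Trial timing against the 20-minute set**

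Inputs from 5.2: 10 s rest, 4 s vocalization, vibration starting after 2 s of vocalization, 50 trials.

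- Trial length: 10 + 4 = 14 s.
- Set length: 50 × 14 s = 700 s = 11.7 min, which is 20 − 11.7 = 8.3 min short.
- Vibration per trial: 4 − 2 = 2 s. Per set: 50 × 2 s = 100 s = 1.7 min.
- If the 4 s is instead counted from vibration onset, a trial is 10 + 2 + 4 = 16 s. The set is then 50 × 16 s = 13.3 min, with 50 × 4 s = 3.3 min of vibration. That is still short of 20 min.

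**4. Trial timing against the total of about 30 minutes**

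Take the vibration-only set as continuous for 20 min. The total is 20 + 1.7 = 21.7 min, or 20 + 3.3 = 23.3 min on the longer trial reading. The shortfall from 30 min is 8.3 or 6.7 min.

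**5. What could close the gaps**

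- *Set length.* 20 min over 50 trials is 1200 / 50 = 24 s per trial. Ten seconds of unstated time per 14-s trial would fill the set.
- *Total exposure.* Section 5.1 says "Subjects will perform voice production tasks before, during and after vibration", and 5.2 labels one assessment as OFF, which suggests that others may be done with vibration on. At the assumed 5 min each, one such assessment gives 21.7 + 5 = 26.7 min and two give 31.7 min. Either could be described as about 30.

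**The case against.** The strongest reply is that the timing in 5.2 is incomplete rather than wrong. Fourteen seconds is a minimum, because nothing says that trials run back to back. Assessments with vibration on could supply the missing exposure. Section 5.2 refers to a timeline figure for the full schedule and the remote part to another; neither is visible in the text reviewed. A line of durations beside the remote figure, including a 10-minute one, shows that it carried timings. The vibration-only schedule, and whether the remote 10 minutes is per set, may be given there.

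This stands for the laboratory timing. A reader might infer that the stated 30 minutes is impossible, or might work backwards to a longer vocalization that yields it exactly. The documents support neither: step 5 shows plausible routes to about 30 minutes, and no longer vocalization appears in the trial description.

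The reply does not rescue the remote text. A figure could say whether 10 minutes is per set, but 10 minutes and five repetitions would still differ from 20 minutes and three.

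It is also fair to say that the vowel difference is minor. Section 15.1 divides break duration by total voiced duration, so extra repetitions mainly affect precision.

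**Conclusion.** The remote section contradicts itself and 5.3. Its vibration period is 10 minutes against 20-minute sets, giving 10 or 20 minutes in total against about 30, and it asks for five repetitions of each vowel against three. This rests on the written text alone, and confidence is high.

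The laboratory timing is a secondary point and calls for clarification. As written, the trials take 11.7 of the 20 minutes. The sets give 21.7 minutes of vibration if the vibration-only set is continuous, against about 30 stated. Unstated time between trials, assessments with vibration on, or the timeline figures may account for the difference.

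A reader might also infer that the pre/post comparison is biased. The documents do not support that: each participant is compared with their own baseline. What is unclear is the dose to which the change belongs, and whether that dose is the same in the two testing modes.

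**What to change.** **Remote section.** Either set the remote set length and vowel repetitions equal to the laboratory's, or delete the claim that the procedures are identical and state the remote dose (per set and in total) and repetitions separately. In the second case, show pre/post results by testing mode descriptively, without a test between modes.

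**Sections 5.2 and 5.3.** State the intended trial timing, including any time between trials, the device mode and schedule of each set, and any assessment done with vibration on. Correct the 20-minute or 30-minute figure if it does not follow.

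**Data.** Record the vibration minutes delivered to each participant.

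**Cost.** Wording changes in three places, one recorded number per participant and, if doses differ, one descriptive table. No extra participants or visits are needed.

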#### 6.0 Data and Specimen Banking

N/A.

#### 7.0 Sharing of Results with Participants

N/A

#### 8.0 Study Population

8.1 Inclusion Criteria:

8.1.1 Patients: Diagnosis of spasmodic dysphonia made through a voice disorder specialist.

8.1.2 Controls:

Healthy adults, aged 18-75 years with no known neurological or orthopedic deficits that may affect speech motor functions.

- 8.2 Exclusion Criteria:
  - 8.2.1 Patients:
  - Regular intake of benzodiazepines
  - Cognitive impairment: score < 27 on Mini-mental state examination; score > 19 on Beck depression inventory
  - Identifies with a neurological or musculoskeletal impairment affecting speech motor function. These impairments may include a form of: Dyskinesia, Dystonia, Essential Tremor, Huntington's Disease, Multiple System Atrophy, Muscle Tension Dysphonia, Parkinsonism, Progressive Supranuclear Palsy, Spasticity, Intracranial Neoplasm (brain tumor), Spinal Neoplasm, Cerebrovascular Accident (Stroke), Mild Traumatic Brain Injury, Intracranial Hemorrhage, Multiple Sclerosis

8.2.2 Controls:

- History of impairments affecting speech function.
- Regular intake of benzodiazepines.
- Cognitive impairment: score < 27 on Mini-mental state examination; score > 19 on Beck depression inventory.
- 8.3 Screening:

Page 16 of 27

SD participants will be screened by [name] at the Fairview Lion's Voice Clinic or [name] at the Park Nicollet Voice Clinic, St. Louis Park, MN. All SD subjects will be assessed by the clinicians using an established protocol [2]. The clinical assessment consists of a questionnaire (CAPE V) [49], clinical speech evaluation and a nasoendoscopic exam. These clinical assessments are part of the routine exam that patients receive for diagnostic purposes. They are not an explicit part of this study.

#### 9.0 Vulnerable Populations

- 9.1 Vulnerable Populations:
  - □ Children
  - □ Pregnant women/Fetuses/Neonates
  - □ Prisoners
  - □ Adults lacking capacity to consent and/or adults with diminished capacity to consent, including, but not limited to, those with acute medical conditions, psychiatric disorders, neurologic disorders, developmental disorders, and behavioral disorders
  - □ Approached for participation in research during a stressful situation such as emergency room setting, childbirth (labor), etc.
  - □ Disadvantaged in the distribution of social goods and services such as income, housing, or healthcare
  - □ Serious health condition for which there are no satisfactory standard treatments
  - □ Fear of negative consequences for not participating in the research (e.g. institutionalization, deportation, disclosure of stigmatizing behavior)
  - □ Any other circumstance/dynamic that could increase vulnerability to coercion or exploitation that might influence consent to research or decision to continue in research
  - □ Undervalued or disenfranchised social group
  - $\Box$  Members of the military
  - $\Box$  Non-English speakers
  - $\Box$  Those unable to read (illiterate)
  - □ Employees of the researcher
  - $\Box$  Students of the researcher
  - $\boxtimes$  None of the above

#### **10.0** Local Number of Participants

10.1 Local Number of Participants to be Consented:

Number of patients with spasmodic dysphonia (SD) will be 20 and number of healthy control subjects (CTL) are 20.

### 11.0 Local Recruitment Methods

Page 17 of 27

#### 11.1 Recruitment Process:

Voice-disordered subjects (SD) will be recruited through our own SD patient database, through [name] at the Fairview Lion's Voice Clinic, or through [name] at the Park Nicollet Voice Clinic, St. Louis Park, MN. Control subjects will be recruited from the community via flyer and will be matched for gender and age to the SD participants.

11.2 Identification of Potential Participants:

SD patients are seen regularly by Drs. [name] and [name] as part of their clinical routine. [name] sees approximately 30-40 patients a month and administers Botox injections as medically indicated. Both clinicians will identify potential participants and inform them about the study possibility. The initial contact to potential participants is made by either [name] or [name] at their respective clinics. We will not access patient databases in either clinic to identify potential participants through the study coordinator. Note that potential participants are regularly seen by Drs. [name]/[name] as part of the ongoing patient treatment (e.g. Botox injections). At these scheduled visits Drs. [name]/[name] will share the study information flyer (see ETHOS section: Recruitment Materials) with potential participants and explain to them the scope of the study. If patients are interested in participating, the contact information of the study coordinator will be shared with the patient, who can then contact the study team. Once the study coordinator is contacted by a potential participant, he will explain the study procedure in detail and will invite participation. If agreeable, a date for obtaining informed consent and data collection is set. Prior to study begin, investigators will obtain and document informed consent from each participant according to21 CFR 50, Protection of Human Subjects (see also section 20.0).

Both Drs. [name] and [name] have legitimate access to patient PHI as part of their clinical work. Relevant PHI (type of diagnosis, disease duration, frequency of Botox injections) will not be shared with the study team of the PI before consent has been obtained and the participant has signed the appropriate HIPAA form.

11.3 Recruitment Materials:

Healthy and SD participants will be invited to the study via flyers that summarize the study and its goals.

11.4 Payment:

Study participants will be reimbursed \$100 for one time in-lab study visit. Study participants will be reimbursed \$50 for remote study.

#### 12.0 Withdrawal of Participants

12.1 Withdrawal Circumstances:

Page 18 of 27

Participants may opt to take a break or withdraw at any time during the study, if they experience discomfort or become fatigued.

Although our preliminary investigation showed that the applied vibration frequency and amplitude is not sufficient to induce a swallowing or gag reflex, we will stop the procedure, if such incidence is observed. Elicitation of a swallowing reflex is not harmful, but its repeated non-volitional elicitation may cause discomfort.

12.2 Withdrawal Procedures:

If such event would occur, we would give the participant the option to adjust the vibration parameters or to completely withdraw from the study. Any data collected up to that point would be destroyed and not used in further analysis.

12.3 Termination Procedures:

Upon reaching the limit of the proposed study population, recruitment will stop and only data analysis will continue. Once the analysis is completed, the de-identified data sets will remain on UMN HIPAA compliant servers. They will form the basis for any scientific publication resulting from the study. We will then orderly terminate the study following the procedures required by IRB.

### **13.0** Risks to Participants

13.1 Foreseeable Risks:

Vibration Risks. The risks in this study are minimal other than the possibility of skin redness over the skin or feelings mimicking numbness over the neck area during trials. These discomforts, if any occurs, usually disappear within minutes after vibration is removed. EEG Risks. There is no particular risk associated with EEG recordings. The procedure is non-invasive and no energy is imposed by the system to the participant. Participants may opt to take a break or stop/withdraw at any time, if they experience any discomfort due the wearing of the EEG cap. Wearable Collar Risks: This risk of using the collar with respect to irritation/rubbing is minimal. Because the textile is chosen from biocompatible material and the collar is not moving during the testing, there is minimal risk associated with it. In addition, because the electronics do not have any contact with the tissue and are enclosed in a housing, the risk of the electronics being affected by moisture/sweat is minimal.

#### 14.0 Potential Benefits to Participants

14.1 Potential Benefits:

Page 19 of 27

There is no direct benefit to participating in this study. At this point, there are no known data that provide conclusive evidence for the effectiveness of laryngeal vibration in reducing voice disorder symptoms.

#### 15.0 Statistical Considerations

#### 15.1 Data Analysis Plan:

Analysis of voice data. Acoustic analysis will follow the methodology described by [50]. Waveform and wide-band spectrograms will be used to identify and measure the duration of the variables. The acoustic signal will be examined for the presence of phonatory breaks and aperiodic breaks. Phonatory breaks are defined as any voiced phonemic segment without sound that is greater than 50ms; the duration of phonatory breaks will be measured. Aperiodic segments will be identified as any voiced phonemic segment that contains non-repetitive cycles that are greater than 50ms; and the duration of the break will be measured. To standardize the duration measures for both phonatory and aperiodic breaks, the sum of the duration of breaks will be divided by the sum of the duration of all voiced segments for each subject. Inter-rater reliability will be measured using Cohen's alpha and intra-rater reliability will use Pearson's r correlation (expected to range between r=.89 to r= .98 according to [50]). For both break types, the absence of phonation or the presence of aperiodicity at the boundary of a syllable or the beginning of a word will not be considered. We will perform a MANCOVA procedure employing all acoustic variables with pre-/posttests as independent factors. If the MANCOVA is significant, separate univariate ANOVAs will be performed on each acoustic variable (dependent) and assessment conditions as a repeated measure (independent) [50]. Appropriate Bonferroni adjustments will account for multiple testing.

Analysis of EEG data. EEG recordings during speech are known to be susceptible to noise from the multiple muscles in and near the head that are involved in speech production. We have been cognizant to this fact and a) designed a simple vocalization task that does not involve complex patterns of muscle activation and b) use modern noise removal techniques that have been successfully applied for the analysis of voice related EEG. [name] is an expert in the analysis of speech-related EEG and will lend his expertise for EEG data analysis, which is based on the widely utilized MATLAB EEGlab toolbox [51]. Space limitation does not permit to describe all processing steps in detail. However, here we outline its major approach. First, to remove motion and electromyographic artifacts, all channels will be filtered (0.5 Hz high-pass and 20 Hz low-pass FIR filter). Second, target events will be extracted and trials containing non-physiological signal amplitudes will be rejected (typically outside [-100 µv 100 µv]). Third, for further objective noise removal the ADJUST algorithm (Automatic EEG artifact Detector based on the Joint Use of Spatial and Temporal features)

Page 20 of 27

will be utilized - algorithm also included in the NIH Neuroimaging Tools and Resources Platform. Finally, an Independent Component Analysis (ICA) will be applied [52]. The ICA statistically decomposes all 64 channels into 64 independent sources of information (components) whose weighted sum is assumed to result in the formation of the recorded data. After this step, the pruned components are combined, generating a cleaner data set. After the ICA weights have been computed, the ADJUST will be employed to detect those independent components, which based on the statistical criteria of the algorithm, were the potential sources of stereotyped artifacts (eye blinks, vertical eye movement, horizontal eye movement, generic discontinuity i.e. inappropriate signals due to noisy channels or muscle activation) [53]. The statistical criteria for removing noise components include temporal kurtosis and spatial average difference [SAD] (from eye blinking), the maximum epoch variance [MEV] and SAD (from vertical eye movements), the MEV and spatial eye difference [SED] (from horizontal eye movements), and MEV and the generic discontinuity spatial feature [GDSF] (from bad channels and muscle activation). After the removal of noise components, a time-frequency analysis will be carried out on all channels of the pruned dataset. The analysis will yield the mean eventrelated changes in the spectral power "ERSP" (from pre-stimulus baseline) for the different frequency ranges at each time instance of all epochs.

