# **STUDY SUMMARY**

Study Title	Effect of Laryngeal Vibration on Voice Quality
Study Design	Single-intervention, pre- posttest design. Subjects
	perform voice production tasks before, during and
	after vibration.
Primary Objective	The purpose of this research is to examine the
	effects of laryngeal vibration on objective markers
	of speech quality in healthy human volunteers and
	people with spasmodic dysphonia, a voice disorder
	affecting the laryngeal muscles.
Secondary Objective(s)	Obtain preliminary data in a limited sample of SD
	patients that show the potential effectiveness of the
	approach after a single application of vibro-tactile
	stimulation (VTS) of the larynx.
Research	Vibro-tactile stimulation of the superficial skin
Intervention(s)/Investigational	surface above the larynx (human voice box)
Agents	
Scientific Assessment	Nationally based non-federal funding organizations-
	National Spasmodic Dysphonia Association
IND/IDE # (if applicable)	NSR IDE
IND/IDE Holder	N/A
Investigational Drug Services	N/A

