#### 1.0 Objectives

#### 1.1 Purpose:

The general aim of the research is to provide scientific evidence that VTS represents a non-invasive form of neuromodulation that can induce measurable improvements in the speech of SD patients. This research addresses a clinical need to develop alternative or auxiliary treatments for a rare voice disorder with limited treatment options. A successful completion of the proposed work will be an important step in advancing laryngeal VTS as a therapeutic intervention for improving the voice symptoms in SD. Specifically, the scientific yield by achieving the specific aims is threefold: First, it will elucidate the unknown neurophysiological mechanism behind laryngeal VTS by documenting the neural changes associated with VTS. Second, it will establish that VTS can improve voice quality in SD. Third, by documenting that laryngeal VTS yields long-term benefits on voice quality in SD patients, it would provide a solid basis for a clinical trial that needs to address open questions on optimal dosage and duration of VTSbased voice therapy, the magnitude of the therapeutic effect across adductor and abductor SD and its long term efficacy.

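### Experts score voice breaks for a pre/post test, but the plan does not mask them to time point or group or randomise scoring order, so a scoring shift of unknown size could pass for a VTS effect

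*Combined protocol and SAP*

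**What the plan says.** - **Who scores.** Section 5.1 sends the recordings "for subsequent acoustic analysis on voice quality by speech analysis experts".
- **How.** Section 15.1: "Waveform and wide-band spectrograms will be used to identify and measure the duration of the variables". It refers the acoustic method to reference 50 and plans inter-rater and intra-rater reliability checks, so it presupposes human raters.
- **Rules that limit judgement.** "Phonatory breaks are defined as any voiced phonemic segment without sound that is greater than 50ms", and a similar 50 ms rule applies to aperiodic segments. For both break types, events "at the boundary of a syllable or the beginning of a word will not be considered".
- **What is tested.** Section 15.1 plans a MANCOVA on all acoustic variables with pre-/posttest as the factor, followed by univariate repeated-measures ANOVAs with Bonferroni adjustment.
- **Design and expected direction.** The Study Summary describes a "Single-intervention, pre- posttest design". Section 1.1 states the hoped-for result: "Second, it will establish that VTS can improve voice quality in SD".
- **File names.** Under Optional remote testing: "The files names comprise only the subject ID and the session number (i.e prestest, set 1, etc". The sentence is part of a statement on privacy. No naming rule is given for in-laboratory recordings.
- **Masking.** No supplied passage says that scorers are masked to time point or group, that files are recoded, or that scoring order is random.

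**The concern.** Time point is the factor being tested, no sham or no-vibration arm is described, and the direction of benefit is stated in advance. If a scorer knows which recording is the pretest, expectation can affect where a segment edge is placed or whether cycles are called non-repetitive. Any resulting shift goes straight into the pre/post contrast and looks like the effect sought.

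The break measures are the only voice outcome with a stated analysis; the 0 to 10 effort rating has none. The protocol intends the results as the basis for a later clinical trial (sections 1.1 and 3.1), so a false signal would carry forward.

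**Working it through.** The plan gives no alpha, power, effect size or SD for the acoustic variables, so there is no figure to reproduce. The check has a textual part and an illustration.

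**1. Does the plan leave room for judgement?** Yes. The 50 ms rule and the boundary exclusions narrow it, but a reader still places edges and judges periodicity. The threshold can also magnify a small difference: a 55 ms segment read 6 ms shorter is 55 − 6 = 49 ms, so it adds 0 instead of 55 ms to the summed break duration.

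**2. Would the reliability checks reveal a time-linked shift?** No. Raters who share an expectation can agree closely with each other and with themselves.

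**3. What could a shift do? (Illustration only.)**

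Inputs: n = 20 SD participants (section 10.1). Assumed: SD participants analysed alone, true change zero, and a scoring shift d, in SD units of the paired difference, of 0.2, 0.3 or 0.5. The documents support no particular d.

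*(a) One paired t-test, two-sided 0.05.* df = 19, critical value 2.093, noncentrality = d × √20, and false-positive rate = P(|T| > 2.093) under the noncentral t distribution.

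| d | d × √20 | False positives |
|---|---|---|
| 0.2 | 0.894 | 13.6% |
| 0.3 | 1.342 | 24.7% |
| 0.5 | 2.236 | 56.5% |

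At 0.025 (Bonferroni over two break types) the rates are 8.1%, 16.2% and 43.9%.

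*(b) Gated analyses, by simulation.* Section 15.1 does not give the form of the MANCOVA, alpha or the number of tests. Assumed: two break measures correlated 0.3, a Hotelling T² gate at 0.05, then at least one univariate test at 0.025.

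- Pre/post version: gate on two differences, then paired t-tests.
- Five-assessment version: pretest, after set 1, Post 2 OFF, Post 20 and Post 60, with an equal shift at all four post assessments. The gate is on eight differences from pretest, followed by Greenhouse-Geisser repeated-measures ANOVAs.

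| Version | d = 0 | d = 0.2 | d = 0.3 | d = 0.5 |
|---|---|---|---|---|
| Pre/post, all participants affected | 3.4% | 11.9% | 23.5% | 59.4% |
| Pre/post, 10 of 20 affected | – | 5.4% | 7.6% | 15.0% |
| Five assessments, all affected | 1.3% | 4.0% | 9.2% | 36.3% |
| Five assessments, 10 of 20 affected | – | 1.8% | 2.4% | 5.3% |

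The number of assessments is itself an assumption: the timeline figure is not shown, and the label Post 2 OFF suggests there may also be assessments with vibration on.

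**The case against.** The strongest reply is that this is an omission. The acoustic method is taken from reference 50, which may include masking and is not among the documents. The break definitions restrict discretion. The protocol describes the work as preliminary and says it is not a clinical trial at this point, and with no sham arm, masking would leave participant expectation, practice and fatigue untouched.

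Much of this stands, and it rules out three stronger readings that a reader might infer:

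- **That scorers see the time point in the file name.** The naming rule concerns files on the remote participant's recorder. Remote testing applies only when a laboratory visit is not feasible, and the number tested that way is not given. Nothing shows what names reach the scorers.
- **That the false-positive risk is large whenever all files are exposed.** In the five-assessment version with every file affected, shifts of 0.2 and 0.3 SD give only 4% and 9%.
- **That recordings made during vibration cannot be masked.** Section 2.2 reports a detectable vibrator signal in pilot vowel recordings made while vibrators were being selected. The revision history shows that a wearable device later replaced the wired one. This supports only that such recordings may reveal themselves.

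The reply does not remove the gap. De-identification is not stated to remove time point, the break definitions still need a reader, and the lack of a masking statement covers in-laboratory recordings as well.

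**Conclusion.** The concern holds as a weakness in the design as written. Experts score the outcome, time point is the tested factor, and nothing in the supplied text masks scorers or randomises scoring order. That is clear from the text. Whether scoring will in fact be unmasked is not known, and no bias has been shown.

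The size of any shift is unknown. The illustrated false-positive rates run from about 2% to 59%, depending on the assumed shift, the share of files affected and the test used. They also rest on an assumed alpha, Bonferroni divisor, MANCOVA form and number of assessments, and on analysing the SD group alone. They show only that a moderate shift could matter.

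The change should be made, because it is cheap and works on stored audio.

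**What to change.** **Fix 1.** Add to section 15.1:

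> Before scoring, all in-laboratory and remote audio files will be renamed with random codes, stripped of timestamps and scored in random order across participants, groups and assessments. A team member who does not score holds the key until scoring is locked. Recordings made during vibration may reveal themselves by the vibrator signal and will be scored and reported separately.

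If scorers are already masked, state this instead.

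Cost: a little file handling and a few sentences, with no extra participants or recordings. Limits: group may still be recognisable from the voice, and participant expectation, practice and fatigue effects remain.

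**Fix 2 (separate and secondary; not evidence of the masking bias).** Cohen's alpha, named in section 15.1, is not a recognised inter-rater statistic, and Pearson's r ignores constant or proportional differences between readings. For durations, report an absolute-agreement ICC with the mean difference and limits of agreement. For presence or absence of a break, report kappa. This costs slightly more analysis work and does not replace Fix 1.
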